# A RANDOMISED CONTROLLED TRIAL TO EVALUATE IMPACT OF DIAGNOSTIC TESTING FOR INFLUENZA, RESPIRATORY SYNCYTIAL VIRUS AND STREPTOCOCCUS PNEUMONIAE INFECTION ON THE MANAGEMENT OF ACUTE ADMISSIONS IN THE ELDERLY AND HIGH-RISK ADULTS.

Name	
------	--

Study Number \_\_\_\_\_

Health Questionnaire (Day 7 Postal- Proxy) English version for the UK

# Script for proxy version of the EQ-5D

(Asking the proxy to rate how he or she, (i.e. the proxy), would rate the subject's health)

We would like to thank you again for agreeing to help us with the above study. As part of this research we are interested in \_\_\_\_\_\_\_''s health today. For this reason we would like you to complete the following short questionnaire and return it to us in the pre-paid envelope provided. We would be grateful if you could complete this questionnaire as soon as possible. Please return it to us in the pre-paid envelope provided.

Please indicate the date on which you completed this questionnaire

\_\_\_\_/\_\_\_/\_\_\_\_

By placing a tick in one box in each group below, please indicate which statements best describe \_\_\_\_\_\_health state today.

Do not tick more than one box in each group

# Mobility

No problems in walking about	
Some problems in walking about	
Confined to bed	
Self-Care	
No problems with self-care	
Some problems washing or dressing himself/herself	
Unable to wash or dress himself/herself	
Usual Activities (e.g. work, study, housework, family or leisure activities)	
No problems with performing his/her usual activities	
Some problems with performing his/her usual activities	
Unable to perform his/her usual activities	
Pain/Discomfort	
No pain or discomfort	
Moderate pain or discomfort	
Extreme pain or discomfort	
Anxiety/Depression	
Not anxious or depressed	
Moderately anxious or depressed	
Extremely anxious or depressed	

	Best
	imaginable health state
To help people say how good or bad a	noulli olulo
nealth state is, we have drawn a scale	100
ather like a thermometer) on which	Ŧ
•	Ŧ
e best state you can imagine is	†
narked 100 and the worst state you	
an imagine is marked 0.	
	
Ne would like you to indicate on this	+
scale how good or bad	80
health is	
oday, in your opinion. Please do this	 
by drawing a line from the box below to	Ŧ
whichever point on the scale indicates	7 0
now good or bad you think the	+
subject's health state is today.	
	
	$6 \stackrel{\bullet}{=} 0$
	Ŧ
	Ŧ
	5
Health today	
	+
	4 •0
	‡
	$3 \stackrel{\bullet}{=} 0$
	+
	Ŧ
	$2\pm 0$
	 
	±
	$1 \overline{\bullet} 0$
	Ŧ
	+
	+
	±
	0
	Worst
	imaginable health state
	noulli sidle

# 28-Day telephone interview with subjects unable to complete postal questionnaires

Name		Stud	y Number
Admission date	//	Discharge date	//
Date of 28 days from	admission date	//	

During your recent stay in hospital you kindly agreed to take part in the above study. As part of this research we would like to ask you a few questions about any health care you have received since you were discharged from hospital.

#### We would also like to ask you a few simple questions about your health today.

**Question 1**. Firstly, we would like to ask you if any of the following health care professionals have visited you in your own home since you were discharged from hospital? Remember, here we are only interested in health care you have received in your own home. Have you seen a PLEASE READ OUT THE LIST BELOW: IF YES, ASK How many times did you see this person?

$\Box_1$	GP	How many times?
$\square_2$	District nurse	How many times?
3	Practice nurse	How many times?
4	Other nurse	How many times?
5	Home care worker/ home help	How many times?

**AT END of LIST ASK**. Apart from the people I have mentioned have you any other health care professionals in your own home? **IF YES, ASK**: How many times did you see this person? **PLEASE KEEP ASKING UNTIL RESPONDENT STATES THEY HAVE SEEN NO OTHER HEALTH CARE PROFESSIONAL**.

6	Other person (please specify)	How many times?
7	Other person (please specify)	How many times?
8	Other person (please specify)	How many times?

**Question 2.** We would now like you to think of any health care professionals that you might have seen outside your own home since you were discharged from hospital. Remember, here we are only interested in health care you have received outside your own home. Have you seen a **READ OUT THE LIST BELOW: IF YES, ASK** How many times did you see this person?

1	Hospital doctor in outpatients department	How many times?
$\square_2$	GP	How many times?
3	Practice nurse	How many times?
4	Other nurse	How many times?
5	A&E department	How many times?

Apart from the people I have mentioned have you visited any other health care professionals outside your home? IF YES, ASK: How many times did you see this person? PLEASE KEEP ASKING UNTIL RESPONDENT STATES THEY HAVE SEEN NO OTHER HEALTH CARE PROFESSIONAL.

6	Other (please specify)	How many times?
7	Other (please specify)	How many times?
8	Other (please specify)	How many times?

**Question 3.** Since your discharge from hospital have you had any extra medicines prescribed for you? Please do not include any medicines you were prescribed in hospital, or any medicines that you regularly received before your stay in hospital. We are only interested in extra medicines that have been prescribed since you were discharged from hospital.

Yes	$\Box_1$
No	$\square_2$

IF YES, ASK How many new medicines have you been prescribed? \_\_\_\_\_

For each new medicine could you tell us the name of this medicine and how long (in days) the prescription was for?

	Name of Medicine	How long for?
1		
2		
3		
4		
5		

**Question 4.** Since your discharge from hospital have you bought any non-prescription medicines 'over-the-counter'; for example, in chemists, supermarkets, or other shops. Please also include any medicines that were bought for you by other people. Again, we are interested only in the period since your discharge from hospital.

**IF YES, ASK** *How many 'over-the-counter' medicines have you purchased or had purchased for you since you were discharged from hospital?* 

For each medicine could you tell us the name of this medicine, the number of items (i.e. packets, bottles, or tubes) and the approximate packet size?

	Name of Medicine	Number of items	Approximate packet size
1			
2			
3			
4			
5			

#### EuroQol

We are trying to find out what you think about your health. I will ask you a few brief and simple questions about your own health state today. I will explain the tasks fully as I go along but please interrupt me if you do not understand something or if things are not clear to you. Please also remember that there are no right or wrong answers. We are interested here only in your personal view.

First I am going to read out some questions. Each question has a choice of three answers. Please tell me which answer best describes your own health state today.

Do not choose more than one answer in each group of questions.

NOTE FOR INTERVIEWER: IT MAY BE NECESSARY TO REMIND THE RESPONDENT REGULARLY THAT THE TIMEFRAME IS TODAY. IN ALL CASES PLEASE INDICATE RESPONSES BY CIRCLING ONE NUMBER ONLY FOR EACH QUESTION.

#### Mobility

First I'd like to ask you about mobility. Would you say you have...

- 1. No problems in walking about?
- 2. Some problems in walking about?
- 3. *Are you confined to bed?*

#### Self-Care

Next I'd like to ask you about self-care. Would you say you have...

- 1. No problems with self-care?
- 2. Some problems washing or dressing yourself?
- 3. *Are you unable to wash or dress yourself?*

#### **Usual Activities**

Next I'd like to ask you about usual activities, for example work, study, housework, family or leisure activities. Would you say you have: ...

- 1. No problems with performing your usual activities?
- 2. Some problems with performing your usual activities?
- 3. Are you unable to perform your usual activities?

#### Pain/Discomfort

Next I'd like to ask you about pain or discomfort. Would you say you have...

- 1. No pain or discomfort?
- 2. *Moderate pain or discomfort?*
- 3. *Extreme pain or discomfort?*

#### Anxiety/Depression

Finally I'd like to ask you about anxiety or depression. Would you say you are...

- 1. Not anxious or depressed?
- 2. *Moderately anxious or depressed?*
- 3. *Extremely anxious or depressed?*

I would now like to ask you to do a rather different task.	Best imaginable health state
To help you say how good or bad your health state	
is, I'd like you to try to picture in your mind a scale	100
that looks a bit like a thermometer. Can you do	Ŧ
that? The best health state you can imagine is	Ŧ
marked 100 (one hundred) at the top of the scale	+
and the worst state you can imagine is marked 0	
(zero) at the bottom.	9 ● 0
	‡
I would now like you to tell me the point on this	+
scale where you would put your own health state	+
today.	8 • 0
iouuy.	+
	+
	Ŧ
	$7 \overline{\bullet} 0$
	+
	+
Your own	
health state	+
	+
today	-
	+
	,±.,
	$4 \stackrel{\bullet}{=} 0$
Finally, we would like to thank you for your help in completing	
this questionnaire.	+
	3 • 0
	‡
	+
	1
	$2 \overline{\bullet} 0$
	Ŧ
	+
	Ŧ
	$1 \neq 0$
	1 + °
	‡
	0
	-
	Worst
	imaginable
	health state

#### HOSPIAL HEADED NOTEPAPER

#### Day 28 postal questionnaire

# A RANDOMISED CONTROLLED TRIAL TO EVALUATE IMPACT OF DIAGNOSTIC TESTING FOR INFLUENZA, RESPIRATORY SYNCYTIAL VIRUS AND STREPTOCOCCUS PNEUMONIAE INFECTION ON THE MANAGEMENT OF ACUTE ADMISSIONS IN THE ELDERLY AND HIGH-RISK ADULTS.

Name	Study Number
Admission date//	Discharge date//
Date of 28 days from admission date	//

During your recent stay in hospital you kindly agreed to take part in the above study. As part of this research we would like to ask you a few questions about any health care you have received since you were discharged from hospital

We would also like to ask you a few simple questions about your health today.

**Question 1.** Firstly, we would like to ask you if any of the following health care professionals have visited you in your own home since you were discharged from hospital? For each type of person, please tick the box if you saw this health care professional and tell us how many times you saw this person. Remember, here we are only interested in health care you have received in your own home.

1	GP	How many times?
$\square_2$	District nurse	How many times?
3	Practice nurse	How many times?
4	Other nurse	How many times?
5	Home care worker/ home help	How many times?
6	Other person (please specify)	How many times?
7	Other person (please specify)	How many times?
8	Other person (please specify)	How many times?

**Question 2.** We would now like you to think of any health care professionals that you might have seen outside your own home since you were discharged from hospital. For each type of person, please tick the box if you saw this health care professional and tell us how many times you saw this person. Remember, here we are only interested in visits you have made to receive healthcare outside your home.

1	Hospital doctor in outpatients department	How many times?
$\square_2$	GP	How many times?
3	Practice nurse	How many times?
4	Other nurse	How many times?
5	A&E department	How many times?
6	Other (please specify)	How many times?
7	Other (please specify)	How many times?
8	Other (please specify)	How many times?

**Question 3.** Since your discharge from hospital have you had any extra medicines prescribed for you?

(Please do not include any medicines you were prescribed in hospital, or any medicines that you regularly received before your stay in hospital. We are only interested in extra medicines that have been prescribed since you were discharged from hospital.)

 $\begin{array}{c|c} YES & \square_1 \\ NO & \square_2 \end{array}$ 

If YES: How many new medicines have you been prescribed? \_\_\_\_\_\_ For each new medicine could you tell us the name of this medicine and how long (in days) the prescription was for? Please place your answers in the boxes below

	Name of Medicine	How long for?
1		
2		
3		
4		
5		

**Question 4.** Since your discharge from hospital have you bought any non-prescription medicines 'over-the-counter'; for example, in chemists, supermarkets, or other shops. Please also include any medicines that were bought for you by other people. Again, we are interested only in the period since your discharge from hospital.

If yes, how many 'over-the-counter' medicines have you purchased or had purchased for you since you were discharged from hospital?

For each medicine could you tell us the name of this medicine, the number of items (i.e. packets, bottles, or tubes) and the approximate packet size. Please place your answers in the boxes below

	Name of Medicine	Number of items	Approximate packet size
1			
2			
3			
4			
5			

**Question 5.** We would now like you to think about your health today. By placing a tick in one box in each group below, please indicate which statements best describe your own health state today.

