## 6.2.2 Monitoring antimicrobial and antiviral treatment (Days 2, 3, 4,5,6 7,8,9, 10, and 28), and other new drugs prescribed for this illness

- The relationship between the results of diagnostic tests and antimicrobial therapy is a key measure. The study nurse will record the name(s), the time when first administered, the dose, frequency of administration, and route of delivery of all newly prescribed antimicrobials/antivirals in the CRF. Subsequent changes in dose, frequency of administration, and route of delivery must be documented, even when the same antimicrobial is prescribed. The number of days that each formulation was prescribed will be documented in the CRF by reference to the Prescription Chart.
- 2. The nature of antibiotic, i.e., whether 'narrow/targeted' or 'extended'-spectrum, will be entered subsequently in the CRF.
- 3. Resource use is a key measure in this study, so the name(s), dose, frequency, and route of administration of newly prescribed drugs (including routinely prescribed medication at a higher dose, such as insulin) and intravenous fluids will be recorded in the CRF, by reference to the Prescription Chart.
- 4. The name(s), dose, frequency, and route of administration of any newly prescribed antimicrobial drugs that are given to the patient on discharge will be recorded in the CRF by reference to the Prescription Chart.
- 5. Details of any antibiotics prescribed for this condition by the GP following discharge will be captured by a Questionnaire (Appendix I, see Pages 60 and 65). Patients will receive a reminder telephone call on Day 28 to return the Questionnaire by post.

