#### 6.2.4 Diagnostic tests, procedures, and other resource implications (Days 2, 3, 4, 7, 10, and 28)

The following resources used by study participants will be recorded in the CRF:

- 1. **Diagnostic tests/procedures** The number and type of all investigations and procedures that were carried out by the medical team, up to a maximum of 28 days (up to midnight of day 28) following admission, will be recorded in the CRF. This information will be obtained following discharge from hospital or death, by reference to APEX and examination of the case-notes and X-rays.
- Additional treatment/support The participant may require additional treatment or support, for example from a medical or nurse specialist, physiotherapist, nutritionists, occupational therapy, etc. This will be identified by reference to the medical records on discharge and recorded in the CRF.
- 3. **Discharge medication** The name, dose, frequency, and duration of any newly prescribed discharge medication (i.e., additional to regular prescriptions) will be recorded in the CRF for discharges occurring within 28 days of admission, by reference to the discharge letter.

- 4. **Hospital follow-up** The nature of further investigations (e.g., Chest-X-ray) and hospital follow-up visits that occur within 28 days of admission will be recorded in the CRF. This information will be captured by a Questionnaire (Appendix I, see Pages 60 and 65).
- 5. General practitioner consultations (Day 28) The number of occasions that patients were seen by their GP or deputising doctor after discharge (up to 28 days following admission), and whether it occurred in the surgery, another medical centre, or in the patient's home will be recorded in the CRF. This information together with the nature of any treatment received will be captured by a Questionnaire (Appendix I, see Pages 60 and 65).

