#### 7.5.2 Financial endpoints

- 1. Costs of diagnostic tests, Costs will be identified for:
  - (a) Rapid near patient test for influenza (Quidel);
  - (b) Rapid near patient test for pneumococcus (Binax NOW),
  - (c) Molecular (multiplex PCR) tests for influenza A and B and RSV A and B
  - (d) 'Prompt' antigen detection test for pneumococcus (Binax NOW), using x25 concentrated urine in the laboratory
  - (e) Culture (blood and sputum) for S. pneumoniae
  - (f) Gram staining of sputum samples
  - (g) Cell culture for influenza A and B
  - (h) Cell culture for RSV A and B
  - (i) Other tests that may be applied, eg immunofluorescence
- 2. Care costs Cost of inpatient stay ( $\pm$  95%CI) will be determined for:
  - (a) All patients in Groups 1, 2, and 3;
  - (b) All patients (in all groups) with (i) influenza, (ii) RSV, and (iii) S. pneumoniae infection, and
  - (c) Patients with (i) influenza, (ii) RSV, and (iii) S. pneumoniae infection in Groups 1, 2, and 3.

For patients who are discharged within 28 days of admission, health care resource use in the period after discharge will be recorded using a simple questionnaire administered in a telephone interview.

- 3. Cost-savings that accrue from earlier use of narrow-spectrum antibiotics, oral therapy, or avoidance, or discontinuation of antibiotics will be assessed in
  - (a) All patients in Groups 1, 2, and 3;
  - (b) Patients with (i) influenza, (ii) RSV, and (iii) S. pneumoniae infection in Groups 1, 2, and 3,
- 4. Economic evaluation of near patient and rapid molecular diagnostic tests will be assessed by two main outcomes measures
  - (a) Cost per case detected,
  - (b) Cost per QALY

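### Question 3 of the Day 28 forms may leave out a GP repeat of the hospital antibiotic, which section 6.2.2 relies on those forms to capture

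*Protocol*

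**What the plan says.** Section 6.2.2 item 5 assigns post-discharge antibiotics to the patient questionnaire: "Details of any antibiotics prescribed for this condition by the GP following discharge will be captured by a Questionnaire". Section 6.2.4 item 5 names the same source for treatment given by the GP: "This information together with the nature of any treatment received will be captured by a Questionnaire". Section 4.1, under resource use after discharge, likewise sends prescriptions up to Day 28 to that form.

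Question 3 of the Day 28 postal questionnaire asks about extra medicines since discharge and then restricts the answer: "Please do not include any medicines you were prescribed in hospital, or any medicines that you regularly received before your stay in hospital". The next sentence reads "We are only interested in extra medicines that have been prescribed since you were discharged from hospital". If the answer is yes, the patient is asked "How many new medicines have you been prescribed", and then for the name and duration of each. The telephone script for patients who cannot complete the postal form carries the same exclusion and the same follow-up.

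The hospital's own take-home supply is recorded separately, under section 6.2.4 item 3: "The name, dose, frequency, and duration of any newly prescribed discharge medication (i.e., additional to regular prescriptions) will be recorded in the CRF".

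Section 7.5.2 item 3 makes savings from earlier narrow-spectrum or oral treatment and from avoiding or stopping antibiotics a financial endpoint in all three groups. Objective 8 in section 2.1 extends costs to 28 days after admission.

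**The concern.** The exclusion is framed by medicine, not by supply. It was presumably written to keep the take-home supply from being counted twice, but its words reach further. A patient treated with an antibiotic in hospital, discharged, and then given a new course of the same antibiotic by the GP has been told to leave out medicines of that kind. The form may then fail to deliver what section 6.2.2 item 5 relies on it for.

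This bears on more than completeness. A GP restart of the same drug is one of the events that would offset a saving from stopping early. Whether a restart can be reported depends on whether the patient received that drug in hospital, which happens after randomisation and is what the rapid tests are meant to alter. Equal completeness across the three groups therefore cannot be taken for granted. Data that were never collected cannot be recovered at the analysis stage.

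**Working it through.** The Protocol states no figure for this point, so there is none to reproduce. The check sets the texts side by side, followed by an accounting identity that shows what would settle the direction.

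**Which GP courses does Question 3 collect?**

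- *A different antibiotic from the one given in hospital, not taken regularly before:* reportable under every reading.
- *Any antibiotic after none was given in hospital, and not taken regularly before:* reportable under every reading.
- *The same antibiotic as in hospital:* excluded by the literal instruction, arguably included by the sentence after it. The list then asks only for new medicines, which points again to leaving it out.
- *A repeat of an antibiotic taken regularly before admission:* in the same position as the previous case.

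Section 6.2.2 item 5 makes no such distinction. It covers any GP antibiotic for the condition.

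**Does another source fill the gap?**

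- Questions 1 and 2 of the Day 28 forms count contacts with the GP and others, not drugs.
- Inpatient drugs come from the Prescription Chart (section 6.2.2), and take-home drugs from the discharge letter (section 6.2.4 item 3). Neither sees a later GP prescription.
- The Day 7 postal forms contain only the EuroQol.
- Section 4.1 says antimicrobials within 10 days of admission will be documented and that sources beyond ward review will be consulted, but it names no GP source.

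**What would the omission do to the comparison?** Let q_R and q_C be same-drug repeat courses per patient after discharge in a rapid-test group and in Group 3, u the share omitted because of the wording (taken as equal in both), and c the cost per course. Recorded cost falls short of true cost by u × c × q in each group. The saving is Group 3 cost minus rapid-group cost, so

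observed saving = true saving + u × c × (q_R − q_C).

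The Protocol gives none of u, q_R, q_C or c. With assumed values, the error in courses per 100 patients per group is 100 × u × (q_R − q_C):

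- u = 1: differences of 0, 0.05 and 0.10 give 0, 5 and 10 courses too much saving.
- u = 0.5: the same differences give 0, 2.5 and 5 courses.
- u = 1 with a difference of −0.05 gives 100 × 1 × (−0.05) = −5, so the saving is understated by 5 courses.

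The sign follows q_R − q_C. More early stopping in the rapid-test groups could raise q_R. More outright avoidance in those groups could lower it, because fewer patients would have a hospital antibiotic to repeat.

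**The case against.** The strongest defence is that Question 3 should be read as a whole. Its opening and the sentence after the exclusion both concern extra medicines prescribed since discharge. On that reading a medicine prescribed in hospital means the hospital's own prescription, and a new GP course is plainly extra. This stands in part: some patients will report the repeat, so non-capture should not be stated as fact. It does not remove the problem, because an explicit instruction to leave something out comes first and the list that follows is limited to new medicines.

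A second defence is that the loss is narrow. A different antibiotic is counted, the GP visit is counted, and section 4.1 undertakes to document antimicrobials in the first 10 days. This also stands: what is at risk is the drug item of a same-drug repeat, and if the section 4.1 undertaking is met after discharge, chiefly between days 11 and 28. With no GP source named, it is unclear how that undertaking would be met for patients already at home.

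A reader might go further and infer that antibiotic savings are overstated. The documents do not support that. Equal omission cancels between groups, and avoidance in the rapid-test groups could push the error the other way.

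A reader might also object that GP dose increases to regular medicines are lost, or that the form does not ask what each drug was for. Neither contradicts the Protocol. Section 6.2.2 item 3 counts higher doses by reference to the inpatient Prescription Chart, and nothing promises the same after discharge. Drug name and duration are enough to identify and cost an antibiotic course.

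**Conclusion.** The point holds as a conflict between the instrument and the section that relies on it. Section 6.2.2 item 5 expects all GP antibiotics for the condition, while Question 3 in both versions gives patients good reason to omit a repeat of the hospital drug, and no other named source records it. Post-discharge antibiotic use and cost may be incomplete, and the between-group cost-savings comparison could be biased because reportability depends on in-hospital prescribing.

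Size and direction are undetermined. The counts per 100 patients shown above rest wholly on assumed repeat rates and omission shares, and serve only to show that the error may be positive, zero or negative. The incompleteness does not depend on its direction.

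**What to change.** In both the postal and the telephone version of Question 3, ask patients to list every antibiotic course prescribed since they left hospital, even if it is the same medicine they had in hospital or took before. Exclude only the supply the hospital issued at discharge. Count the courses so reported in the antibiotic cost-savings endpoint (section 7.5.2 item 3) and in the 28-day costs.

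The cost is a rewording of one question on two forms and a minor amendment. The question becomes slightly longer, and some patients will list take-home supplies, which can be removed against the discharge medication in the CRF. The rewording cannot repair answers already collected with the present form; for those patients the report should say that same-drug repeats may be missing.
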